Safety and tolerability of tumor treating fields (TTFields) combined with chemoradiation in newly diagnosed glioblastoma (UNITY)

Protocol number:	UNITYGBM01
Phase:	I
Investigators:	[name] (PI) [name] [name] [name] [name]
Protocol version:	4.0
Release date:	19MAY2020

Revision history:

Version Number	Version Date	List of Changes
1.0	25SEP2017	N/A
2.0	30JAN2018	
Given that some patients likely will not have their MGMT result by the time of enrollment into the study, MGMT status will not be a cause for exclusion. MGMT results will be used for stratification only.
 
In addition to the first safety lead in cohort, an additional safety stop will be incorporated when half of the study (15 patients) have completed trimodal therapy with TTF, temozolomide, and radiation phase, with another interim analysis before proceeding to the complete enrollment of 30 patients.
 
Revised eligibility criteria to patients 22 years of age or older to match Optune indications (as opposed to age 18 and above).
 
Removed from eligibility: Neurologically stable for at least 14 days prior to first use of TTField therapy. This is vague and already represented by performance status. As long as a potential subject has KPS 70 or greater, they are able to participate.
 
Added consistency: Patients with other significant cancer within the prior 3 years are excluded.
 
Clarified compliance requirement: Patients who are using the TTField treatment less than 75% of the minimum recommended usage of 18 hours a day on average as assessed monthly (13 hours a day or less) unless per officially instituted dose

	
reduction may be discontinued from therapy at the discretion of the investigator or sponsor.
 
Changed schema to show RT dose remodeling BEFORE enrollment and now includes the 2 safety lead-ins.
 
RT should be started within 2 weeks of starting TTF therapy (to give more flexibility to logistics of starting RT).
 
Corrected inconsistency with steroid dosing requirements: Patients can be on high dose steroids after surgery but must have tapered down to 8mg or less of dexamethasone or bioequivalent within 7 days after enrollment.
 
During the study, patients can be discontinued from study therapy at the discretion of the investigator, if they are requiring more than 8mg daily of dexamethasone (or bioequivalent dose) for 7 consecutive days at any given time.
 
Dosimetry start date: March 1st, 2018.
 
Screening start Date April 15th, 2018.
 
PJP prophylaxis will be a recommendation only, and each site may opt to follow their institution protocols.
 
Added clause to allow for initiation of TMZ up to 7 days after start of RT to not count as deviation.
 
Corrected – Neuro exams at week 3 and 6 will be done alongside weekly skin exams during RT phase.
 
Clarified use of novocure device support specialist. This is not a study procedure per se, but is standard practice for all patients on TTField therapy to have access to a device support specialist to troubleshoot use of the device and extract compliance data from the device.
 
Given that the safety and tolerability of adjuvant therapy with ttfields combined with temozolomide was reported in EF-14, this will not be reproduced here. DLT and TRAEs will be monitored and analyzed in the window of greatest concern from start of trimodal therapy to 8 weeks after completion. The use of adjuvant TTFields with temozolomide after that will proceed as per the standard of care. Secondary endpoints (imaging response, PFS at 6 months, median OS overall and at 2 years and duration and compliance of TTF use) will continue to be monitored beyond the trimodal therapy phase.
 
Added statement that transducer arrays must be off the skin during

--	---

		weekly skin checks in trimodal therapy to make the logistics explicitly clear.
2.1	31JAN2018	
Updates to Day 1 of Cycle 2 to allow for final toxicity monitoring 8 weeks after trimodal therapy phase.
 
Statistical considerations updated to remove redundancies and address intention-to-treat analyses.

2.2	23MAY2018	
Corrected DLT review of 15 subjects to read second review instead of initial review.
 
Added language to allow for continued enrollment in trial if study treatment is withdrawn for observational purposes to perform the intention-to-treat analysis.
 
Corrected inclusion #13A to 3-4 weeks (21 to 28 days) for resection, 2-4 weeks (14-28 days) for biopsy. Also corrected this in the pre-treatment period text.
 
Corrected inclusion #13B to include timing of RT start from biopsy date.
 
Added HIV+ to exclusion #2.
 
Clarified that both MGMT and IDH to be reviewed at each subsequent visit post screening until resulted.
 
Removed text from study enrollment visit and treatment period that stated all study related treatments must be initiated no later than 14 days after the Day 1 clinic visit. This could be 21 days after Day 1 if all treatments started on the last day of each window in the sequence of initiating trimodal therapy section.
 
Removed disease assessment/extent of measurable disease from Day 1 of trimodal therapy due to lack of MRI at this time point.
 
Clarifying text added that adjuvant therapy phase falls 4 weeks after the completion of radiation therapy.
 
Updated text to read “criteria for removal of study therapy” from “withdrawal from therapy” to reference correct protocol section title.
 
Clarified that disease assessment/extent of measurable disease and objective response assessments at Day 1 of Cycle 2 will be based on MRI completed at Day 1 Cycle 1 due to absence of MRI at Day 1 Cycle 2, as this is the last visit of the Study Period.
 
Added clarifying text that disease assessment/extent of measurable disease with clinical response or deterioration and objective response

		
assessments to be completed during the Long-Term Follow-up Period only when an MRI was completed since last review/contact.
 
Removed ORR assessment from Long-Term Follow-up Period since this will be calculated during data analysis, not collected per patient.
 
Added text to dose modifications during TTField therapy to clarify when to up-titrate due to non-hematologic toxicity events and allow for investigator discretion.
 
Appendix 3 updated to reflect above noted changes.

3.0	28AUG2018	
The following revisions were made per FDA recommendations:
 
Study Objectives: the secondary objective have been revised.
 
Study Design: Exploratory analysis of radiation dosimetry has been clarified to occur prior to any patient enrollment
 
Eligibility Criteria: Inclusion criterion #9 has been revised to limit consenting permissions to the patient.
 
Exclusion criterion #16 has been added to prohibit patients allergic or unable to have gadolinium contrast dye with MRI.
 
Exclusion criterion #17 has been added to prohibit patients with aneurysm clips or implanted metal objects in the brain.
 
Exclusion criterion #18 has been added to prohibit patients with significant skin breakdown.
 
Clinical Trial Related Procedures; Treatment Modalities: Training of the patient on the use of Transducer Array Layout map, and the placement of arrays has been added.
 
Dose Modifications: Guidance on skin toxicity has been updated.
 
Radiation Therapy without interruptions: text has been updated per updated skin toxicity guidance.

3.1	10SEP2018	
The following revisions were made to incorporate the clarifications from the Protocol Clarification Letter (PCL) dated 06JUN2018 that accompanied protocol version 2.2. These edits did not make it into the 3.0 version of the protocol inadvertently:
 
Removal of PI, [name], as the Data Safety Monitoring Committee Chair. Chair responsibility will be shared by the three committee members.
 
Clarification that the PI and study manager will facilitate the DSMC meetings as non-members.

		
The lead-in phase report will be reviewed by all of the DSMC members due to the removal of the Chair.
 
Death events will be reported to the PI, [name], or designee, Regulatory Manager, [name], due to the removal of the DSMC Chair.
 
Death due to disease progression need not be reported to the PI or designee, not the study monitor, as the study monitor is not the designee.
 
The following additional edits were made:
 
Corrected Data Safety Monitoring Board to Data Safety Monitoring Committee for consistency throughout protocol.
 
Removed INC#8, as EXC#10 describes a different steroid taper timeframe that is more appropriate as eligibility criteria. INC#8 described discontinuation criteria.
 
Removed INC#13B, as this describes timing of events after enrollment, so not true eligibility criteria. Timing of surgery or biopsy to enrollment and initiation of TTField, RT, and TMZ after enrollment already described.
 
INC#13A changed to INC#13 (A and B no longer necessary).

4.0	19MAY2020	
Added co-investigator from UCSF who replaced a prior co-investigator who was removed.
 
Clarified that biopsy may be done alone without resection of GBM.
 
Added that a post-procedure cranial CT may be used instead of an MRI if biopsy completed alone without resection if there was a MRI within 14 days pre-biopsy. This is more in line with potential imaging used as part of standard care. Removed window that this imaging must be done within 72 hours, as this is not realistic per standard care. This language also reflected in the updates made to INC#11.
 
INC#8 changed to allow for a legally authorized representative.
 
INC#12 window changed for surgery from 3-4 weeks to 3-6 weeks (21-28 days to 21 to 42 days). This is more in line with standard care.
 
EXC#2 updated to include active Hepatitis B and active Hepatitis C, and clarified that these illnesses noted in criteria are by history only (not testing for them during trial, removed Hepatitis B labs from screening procedures).

	
EXC#5 updated to add the language regarding prior cancer history exceptions that were previously noted in EXC#13 (now #14), as this is the more appropriate criteria to list these items. Removed from EXC#14.
 
EXC#10 updated to clarify timeframe is calculated off of Day 1.
 
Removed “baseline” throughout text, as this was confusing when this occurred.
 
Moved third bullet from EXC#11 to a new criteria (new EXC#12), as non-hematological toxicity did not fit in lab abnormalities criteria.
 
EXC#14 (prior #13) updated to clarify that significance and stability are per investigator discretion.
 
EXC#16 (prior #15) updated since legally authorized representative now allowed. Added text that patient must be willing and able to complete study procedures, per investigator discretion.
 
INC#19 (prior #18) updated to clarify that the significant skin breakdown is being monitored on the scalp.
 
Added INC#20 to clarify that patients need to be able to receive standard care radiation therapy and can only receive hypofractioned radiation due to age and poor performance status, per investigator discretion.
 
Updated anticipated start dates, as there were contract delays that delayed being able to start dosimetric testing and analysis and site activations.
 
Reworded the screening window period for clarity, window is unchanged.
 
Added typical turnaround time for treatment planning from Novocure (5 business days) to screening for clarity.
 
Clarified that radiation oncology initial clinical visit and planning for therapy must be scheduled during the screening period, if not already completed at the time of screening. Scheduling required only during this time period, may occur post Day 1.
 
Clarified that Day 1 the clinic visit, not necessarily the day TTField is started. Day 1 is when enrollment occurs.
 
Rearranged order of treatments (TTField therapy, RT, TMZ) language from the Study Enrollment section to the Treatment Period section, as this is less confusing this way and does not need to be repeated twice in

--	---

	
the protocol.
 
Added language to the Treatment Modalities section and Clinical Trial-Related Procedures section specifying that the transducer arrays will need to be replaced at study visits that require them to be removed to complete a protocol required procedure (MRIs and skin exams at specified visits).
 
Added language to the Treatment Period section that was present in the treatment modalities section for consistency.
 
Added a diagram depicting the sequence of starting trimodal therapy for added clarity.
 
Added that the procedures listed in the Trimodal Therapy, Day 1 section are to be completed before initiating TTField. Added text so order of events is clear.
 
CBC and chemistry labs at Day 1 do not need to be repeated if these screening labs were collected within 14 days of Day 1. This eliminates the need for duplicate testing when there is not anticipated to be a significant change in that short of a timeframe.
 
Removed phosphorus from the chemistry labs, as this is not a standard part of the site's chemistry panel and needs to be ordered separately. This is not ordered for standard care, so removed.
 
Removed details of toxicity from TTField from skin exam at Day 1, as therapy will not have been initiated and this is not an applicable assessment at this time point.
 
Clarified that the device support specialist may visit the patient in the clinic, not just at their home.
 
Removed text from Day 8 that was redundant regarding when to start RT/TMZ and regarding offsetting calendar procedures, as this was not accurate considering there are windows for when to start study treatment.
 
Removed language regarding PJP prophylaxis from the Day 8 visit and moved it to the treatment modalities TMZ section. This is a more appropriate section, as it is a recommendation and not required at a specific study visit.
 
Added a +7 day window for continuing RT and TMZ past day 49, as clinically appropriate. This follows standard treatment.

--	--

1. OVERALL SYNOPSIS OF THE CLINICAL TRIAL

Title:	Safety and tolerability of tumor treating fields (TTFields) combined with chemoradiation in newly diagnosed glioblastoma (UNITY)
Device:	Optune™ (200kHz output frequency)
Study Objectives:	
Primary Objective: The primary objective is to determine the safety and tolerability of using TTFields concurrent with standard fractionated radiotherapy and temozolomide (TMZ) chemotherapy followed by adjuvant therapy.
 
Secondary Objective: The secondary objective is to report clinical outcomes (overall survival, progression free survival, imaging response, and duration and compliance of TTF use) after the tri-modal therapy.
 
Exploratory Objectives:
 
 1. To explore dosimetric influences of radiation delivery on dose distribution with TTFields arrays as a representation of normal treatment conditions. 2. To explore the feasibility of producing a high-quality mask for radiation planning with TTFields arrays in position. 3. To explore the source of skin toxicity.
Study Design:	
The study is an open-label pilot study in newly diagnosed GBM patients following surgery. Patients (≥ 22 years) with histologically confirmed GBM in the supratentorial region and a KPS $\geq 70\%$ are eligible to participate. Patients must have had MGMT testing performed locally for stratification purposes to participate, but specific MGMT result (positive, negative, or indeterminate) shall not be a cause for exclusion. Eligible patients will be receiving treatment with TTFields starting about 1 week prior to radiation. In addition to TTFields, they will receive radiation and temozolomide at a dose and schedule conforming to the standard of care. The expected toxicity is skin related and patients will be followed closely for weekly skin and neurological examination during the DLT window throughout radiation therapy and then for 8 weeks afterwards to capture any delayed toxicity as they begin adjuvant therapy per the standard of care. As long as tolerated and their conditions remain stable, patients shall continue the experimental therapy up to 24 months per the standard of care.
 
The study incorporates three stages of recruitment to confirm the safety of combining TTFields therapy with concurrent chemoradiation: a safety lead-in cohort of the first 6 patients enrolled, a second safety lead-in cohort of the first 15 patients enrolled (half of the total enrollment), and an expansion cohort with 15 additional patients. For the lead-in cohorts, a safety interim analysis will be performed 4 weeks after radiation of the

	last patient and will need to pass a pre-specified stopping rule before the next stage of recruitment can begin. Safety within the DLT window and efficacy analyses will be performed on all subjects at the end of the study. An exploratory analysis of radiation dosimetry will be performed by phantom modeling incorporating the TTFields electrode arrays prior to any patients being enrolled.
Study Hypothesis:	TTFields has been shown to be safe and efficacious in large trials with glioblastoma patients in combination with adjuvant temozolomide but concurrent use together with trimodal therapy has not been examined in clinical trials. Our primary hypothesis is that the TTFields treatment, if initiated concurrently along with radiation and temozolomide therapy, would not significantly alter the safety profile. Secondarily, continuation of early initiated TTF along with adjuvant temozolomide treatment as per the standard of care would increase progression and overall survival. The primary hypothesis is safety and will be tested directly in this trial, but the secondary hypothesis would be assessed only with preliminary observations and need validation in a larger trial that is statistically powered for that investigation.
Sample Size:	30 patients total, 6 included in the first safety lead-in and 15 in the second safety lead-in.
Study Population:	Patients with newly diagnosed histologically confirmed glioblastoma after maximally safe resection, with MGMT methylation status in process, are eligible for enrollment.
Primary Endpoint:	The primary endpoint is safety and tolerability of the combined use of TTFields added to standard chemoradiation and TMZ.
Secondary Endpoints:	Our secondary endpoints will be progression-free and overall survival, imaging response by RANO criteria, and duration and compliance of TTF use.

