To form a reasonable basis of safety for enrolling the expansion cohort of patients, this study will incorporate two safety lead-ins using the first 6 patients and the first 15 patients (50% of the expected total number of patients) to assess the feasibility, safety and tolerability of combining TTFields therapy with concurrent chemoradiation (concurrent enrollment allowed). The safety cohorts will receive TTFields therapy in addition to standard of care. Variations in daily patient positioning will be recorded. Any treatment related adverse effects will be measured, assessed, and graded during the dose-limiting toxicities (DLT) period, from the beginning of therapy until 8 weeks after completion of radiation therapy to capture any potential delayed toxicity following combination (Trimodal) therapy with radiation, temozolomide, and TTFields therapy. DLT include any severe or life-threatening treatment-related adverse effects that preclude further administration of the study treatments, such as radiation, temozolomide, or continuation of TTFields therapy. The DLT assessment period will be limited to the time from start of TTFields through 8 weeks after RT's completion.

The first lead-in cohort will include the first 6 patients to finish the DLT period and be assessed by investigators. If a DLT occurs in 2 or more of the 6 patients, then the study will not move forward and may re-consider the goal dose of TTFields therapy in the main cohort to be reduced by 50% (one out of every two weeks off) and only increased to the standard usage of

continuous treatment 4 weeks after completion of radiation therapy. If a DLT occurs in less than two patients, the study will proceed with the second safety lead-in.

The second lead-in cohort will include the first 15 patients (6 from the first lead-in and 9 additional) to finish the DLT period and be assessed by the Data Safety Monitoring Committee (DSMC). If a DLT occurs in 5 or more of the 15 patients in the second safety cohort, then the study will not move forward with the expansion cohort and may re-consider the goal dose of TTFields therapy in the main cohort to be reduced by 50% (one out of every two weeks off) and only increased to the standard usage of continuous treatment 4 weeks after completion of radiation therapy. If a DLT occurs in less than five patients, the study will proceed with the final expansion cohort.

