Two weeks after trimodal therapy, patients will receive a skin exam, scalp assessment and neurologic exam at Day 64 and will also be monitored at 4 weeks (Day 1 of Cycle 1 of adjuvant TMZ) and 8 weeks (Day 1 of Cycle 2 of adjuvant TMZ) after trimodal therapy to assess for post treatment toxicity that may be delayed. After conclusion of the DLT window, the treatment of

patients will be carried out per the standard of care in addition to continued TTFields therapy, as outlined in the clinical trial-related procedures section. The trial will then follow the clinical outcomes including duration of TTF use, completion of 6 cycles of temozolomide, and progression free survival at 6 months, and median overall survival and overall survival at 2 years.

Primary Study Endpoints

- Rate of treatment-related adverse events (TRAЕ)
- Rate of treatment-related severe adverse events (TRSAЕ)
- Rate of Dose-limiting toxicity (DLT)

Given that the primary objective of this study is to determine the safety and tolerability of adding TTField therapy to combined chemoradiation, our primary endpoints are related to safety as follows: Identify the rate of treatment-related adverse events as well as the rate of any severe adverse events during the combined treatment period and up to 8 weeks afterwards. For the same time frame, we will also document and assess the rate of dose-limiting toxicities. Safety of combined adjuvant treatment with TTFields and TMZ chemotherapy outside of the initial radiation is not a primary objective and will not be formally assessed in this study. The above endpoints will be assessed initially in the interim safety analyses involving the safety lead-in cohorts and then also in the main expanded cohort for the final analysis. See statistical methods for further details of the planned analysis. For any skin toxicity grade II or greater, we will also investigate and document, if apparent, whether this was related to the adhesive vs the ceramic disc component of the device.

Secondary Study Endpoints

- PFS6
- Overall survival (median OS and rate of OS at 2 years)
- Objective response by modified RANO criteria
- Median duration of TTFields use and rate of TTF compliance

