In the event of a dose-limiting toxicity, the subject will be discontinued from treatment and followed for toxicity assessment and management and a joint decision will be made by the investigator and sponsor whether to adjust the dose or schedule for other subjects or permanently close the study for safety. In the event that more than 33% of subjects experience a DLT, the study cannot continue unless a modification is made to the level of the particular treatment to which that adverse event is definitely attributable. As preliminary safety stops, the study will include two safety lead-ins receiving TTFields with concurrent chemoradiation. These initial 6 and then 15 subjects will undergo interim analyses after completion of chemoradiation to determine if the expanded cohorts should be permitted enrollment as planned or if a dose reduction in TTFields of 50% of the scheduled use is warranted for safety.

Subjects will continue to receive study treatment until confirmed tumor progression, unacceptable toxicity, or other discontinuation criteria as described; subjects MUST discontinue investigational product (and non-investigational product at the discretion of the investigator) if they meet criteria for removal from study therapy as referenced in that section.

Toxicity related to TTFields treatment: Treatment-related adverse events (TRAEs) and severe treatment-related adverse events (STRAEs) will be assessed in the following ways.

- Patients will be evaluated by a neuro-oncologist or radiation oncologist for potential skin toxicity from TTFields therapy. Routine skin care recommendations will be provided, including use clobetasol cream prior to electrode placement and adjusting array placement to avoid continued site irritation. If there are concerns by investigator, the subject will be referred to a dermatologist for specialized evaluation. Neurological and general physical evaluations as well as laboratory assessments will also be conducted by a neuro-oncologist or radiation oncologist to identify other potential toxicities.
- In addition to clinic visits and interventions, Patients will also be supported by a technician from Novocure for device troubleshooting and compliance checks.
- All other adverse effects, either mild, or serious, will be triaged by a physician in coordination with the primary investigators of the study.

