8. STATISTICAL CONSIDERATIONS

Interim analyses of the first and second safety lead-in cohorts will be performed using data collected from the beginning of the study to eight weeks following trimodal therapy for each patient. Patient characteristics will be summarized using means, standard deviations, medians, interquartile ranges, counts, or percentages, as appropriate. Primary endpoints will be summarized using counts and percentages of patients who experienced a treatment-related adverse event, treatment-related serious adverse event, or DLT for safety and stopping rules.

In the second interim analysis, the percentage of patients with inconclusive MGMT methylation status will also be summarized. Patients with inconclusive MGMT methylation status will be removed from the final study analysis, so we will use this percentage to assess the number of additional patients that need to be recruited to meet our sample size requirement of 30 patients. For example, if 2 out of 15 patients have an inconclusive MGMT methylation status at this stage, we will recruit 4 additional patients to meet the sample size requirement.

Using the intention-to-treat approach, the final analyses will be performed on all patients having received at least one day of use from the study device. Patients with an inconclusive MGMT methylation status will be excluded. Patient characteristics will be summarized using

means, standard deviations, medians, interquartile ranges, counts, or percentages, as appropriate.

Primary endpoints will be summarized using counts and percentages of patients who experienced a treatment-related adverse event, treatment-related serious adverse event, or DLT will be reported overall and by event type following trimodal treatment and 8 weeks thereafter to capture any later appearing toxicities. A subgroup evaluation by MGMT methylation status (methylated vs unmethylated) will also be performed.

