Y: Day 1 of the first 2 cycles of adjuvant therapy will fall within the DLT window with continued skin exams (Cycle 1 Day 1 and Cycle 2 Day 1). The subsequent cycles with post-TMZ maintenance TTField therapy will proceed per the standard of care (minimum of 6 cycles, up to 2 years). For continued participation in the trial, patients must continue to follow up every 2-3 months with a repeat MRI of the brain.
Z: To include PFS and OS.
AA: Monitor adverse events through 8 weeks post-RT/TMZ (through Day 1 of first cycle of Cycle 2).
BB: To be stopped post Day 43 visit on Day 49 (+ 7 days, if clinically appropriate).
CC: To be assessed if MRI completed per SOC since last review/contact.
DD: Time that must have elapsed prior to study enrollment (Day 1): 3-6 weeks (21-42 days) from time of definitive surgery or 2-4 weeks (14-28 days) from the time of biopsy for those who were only able to safely have a biopsy and not full resection.
EE: Use MRI from Day 1 Cycle 1 for assessment.
FF: To be completed monthly, may not be available at each visit.
GG: If indicated, per investigator discretion.
HH: Transducer arrays will need to be removed/replaced to complete.

**Please note, the above notations can be found in the body of the protocol, but are listed here as well with the intent of making the study calendar easier to follow.*

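### The DLT counted by the 2-of-6 and 5-of-15 stopping rules has no single definition, and the synopsis times each safety look 4 weeks before the 8-week DLT window closes

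*Combined protocol and SAP*

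**What the plan says.** **What counts as a DLT.** Four places bear on this.

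- Section 6, Safety Lead-ins: severe or life-threatening related effects that prevent further giving of a study treatment.
- Section 7a, opening: severe or life-threatening related toxicity that prevents a specified dose of a study treatment, including TTFields at its standard level and schedule. The grading scale in Section 7 calls Grade 3 severe.
- Section 7a, list: non-haematologic toxicity printed as Grade > 3, and Grade 3-4 radiation-induced skin changes that last more than 7 days and do not improve with management.
- Section 6, device dose modifications: Grade 3-4 non-haematologic toxicity leads to half-schedule use, with resumption possible on improvement. It is named a DLT when TTFields cannot be resumed within 1 month and has to be stopped. For Grade 3-4 skin toxicity during radiotherapy, the radiotherapy section adds a break of at least 1 week.

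Section 7a then takes a subject with a DLT off treatment. The temozolomide section stops that drug for Grade 3/4 non-haematologic toxicity in the trimodal phase (alopecia, nausea and vomiting excepted).

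**When the looks are held.** Synopsis: "For the lead-in cohorts, a safety interim analysis will be performed 4 weeks after radiation of the" last patient. The same synopsis follows patients "during the DLT window throughout radiation therapy and then for 8 weeks afterwards to capture any delayed toxicity". Section 6: "The first lead-in cohort will include the first 6 patients to finish the DLT period and be assessed by investigators". Section 8: "Interim analyses of the first and second safety lead-in cohorts will be performed using data collected from the beginning of the study to eight weeks" after trimodal therapy, for each patient. Appendix 3, note AA: "Monitor adverse events through 8 weeks post-RT/TMZ (through Day 1 of first cycle of Cycle 2". Section 7a gives no interval: "These initial 6 and then 15 subjects will undergo interim analyses after completion of chemoradiation". Under the primary endpoints, Section 6 defers to Section 8: "See statistical methods for further details of the planned analysis".

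**The concern.** One DLT count drives the 2-of-6 and 5-of-15 rules (Section 6), the 33% limit (Section 7a), the report to the DSMC (Section 7) and a primary endpoint. Skin toxicity is the toxicity the synopsis expects, and it is where the definitions diverge. At the first look a single patient separates 1 of 6 (proceed) from 2 of 6 (do not move forward). If the same course of events can be coded either way, the trial's main safety decision and its headline safety rate depend on which paragraph the coder had open.

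The timing conflict acts on the same count. A look at 4 weeks would apply the rule to patients who have not yet finished the first adjuvant temozolomide cycle or had the Day 106 toxicity visit.

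**Working it through.** **Consistency of the plan's own figures.** 2/6 = 5/15 = 33.3%, just above the 33% limit, so the thresholds agree with each other. Radiotherapy ends about Day 49: 49 + 28 = 77 (stated Day 78 ± 5) and 49 + 56 = 105 (stated Day 106 ± 5). The documents give no operating characteristics for the rules.

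**Definition: three cases, each attributed to TTFields or the combination, with "> 3" as printed**

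| Case | Opening of 7a | List in 7a | Device text, Section 6 |
|---|---|---|---|
| A. Grade 3 skin reaction in radiotherapy, Grade 2 by day 6; break, reduced use, then full use | DLT if a break or reduction counts as preventing the standard schedule | No (not over 7 days) | Not named a DLT |
| B. Grade 3 skin reaction, 10 days without improvement; TTFields resumed in week 3 | As for A | DLT if radiation-induced | Not named a DLT |
| C. Grade 3 non-haematologic, non-skin event that ends temozolomide | DLT | No | Not applicable if the device continues |

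In case B, Section 7a takes the patient off treatment, while Section 6 provides reduced use and resumption. In case C, the Safety Lead-ins text agrees with the opening of 7a against the list.

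**How often a disputed skin case could arise.** Section 8 expects severe skin irritation in 5% (2% in EF-14). P(at least one in n) = 1 − (1 − a)^n.

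- a = 0.05: n = 6, 1 − 0.95^6 = 0.265; n = 15, 1 − 0.95^15 = 0.537.
- a = 0.02: 0.114 and 0.261.

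These are ceilings for the skin part, because some such events would be DLTs under every text.

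**Effect on the rules.** With per-patient DLT probability p:

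- Look 1: P(X6 ≥ 2) = 1 − (1 − p)^6 − 6p(1 − p)^5.
- By look 2: add the sum over a = 0, 1 of P(X6 = a) × P(X9 ≥ 5 − a).

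The undisputed risks (10%, 20%) are assumptions.

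| p | Look 1 | By look 2 |
|---|---|---|
| 0.10 | 0.114 | 0.114 + 0.003 = 0.118 |
| 0.15 (10% + 5%) | 0.224 | 0.224 + 0.016 = 0.239 |
| 0.20 | 0.345 | 0.345 + 0.039 = 0.383 |
| 0.25 (20% + 5%) | 0.466 | 0.466 + 0.068 = 0.534 |

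A further 2% on top of 10% gives 0.156 at look 1.

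**Timing.** The Enrollment Plan (Section 6) gives 4-8 weeks for the first six entries. Assume even entry, equal radiotherapy duration, DLT risk 1/3 and constant hazard over 105 days, so F(t) = 1 − (2/3)^(t/105). Look 1 falls 77 days after the last entry.

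- Entry over 28 days: follow-up 77, 82.6, 88.2, 93.8, 99.4, 105 days, so 5 of 6 windows are incomplete. F = 0.257, 0.273, 0.289, 0.304, 0.319, 0.333; P(≥ 2) = 0.571.
- Entry over 56 days: 77, 88.2, 99.4, 105, 105, 105 days, so 3 of 6 are incomplete; P(≥ 2) = 0.603.
- Full window for all six: 0.649.
- If instead 80% of DLTs occur by Day 49 and the rest evenly after: 0.615 and 0.629.

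**The case against.** **The list in Section 7a is the operative definition, and the device text only adds a trigger.** This is the best defence, and the list is worded as the definition. But no passage says that the device criterion is additional, and it is not in the list. Nor does this reading remove the clash in case B between stopping treatment and resuming it.

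**The sign may have been meant as ≥ 3.** Then case C falls, because every text counts it. The skin conflict remains: a Grade 3 reaction would be a DLT at once under the general criterion, yet the device text lets it go to reduced use and resumption. A reader might claim both that case C is missed and that the 7-day condition is empty. The documents do not support both, since each needs the opposite reading of the sign.

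**Central oversight would even out coding.** Grade 3 and higher events go into one system, the principal investigator reviews all adverse events, and the DSMC report covers events as well as DLTs. That lowers the risk of divergence between sites, but it supplies neither a single definition nor an adjudication step. It is also true that 2 of 6 is not automatic closure: Section 6 allows the device schedule to be reconsidered.

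**Stronger timing readings.** From "combining TTFields therapy with concurrent chemoradiation (concurrent enrollment allowed", a reader might infer that recruitment can run past a look. The documents exclude this. The synopsis requires the rule to be passed before the next stage, the Enrollment Plan places expansion after the interim analysis, Section 7a makes expanded enrolment depend on the looks, and Section 7 requires DSMC approval first. Section 7a's phrase on completion of chemoradiation is not a third conflict either, because it states no interval.

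**Conclusion.** The plan is wrong as written on both parts, and they differ in weight.

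The definition is the main point and needs correction before the rules are applied. The skin criterion and discontinuation in Section 7a cannot be squared with the reduce-and-resume path and one-month DLT in Section 6, under either reading of the sign. The documents do not say how many events would be disputed. At the plan's 5%, at most 26% of first lead-ins and 54% of 15-patient cohorts contain a disputed skin case; other Grade 3 events could add to this. The rise in stopping from 11% to 22% at look 1, and from 12% to 24% by look 2, illustrates sensitivity. It rests on the assumed 10% undisputed risk and on every added 5% being disputed, and it is not a forecast.

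The timing is a correction to the synopsis, which is the outlier. If it were followed, the 2-of-6 rule would stop 57-60% of the time instead of 65% at an assumed DLT risk of 1/3 with constant hazard, and the loss is smaller if DLTs come early.

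**What to change.** 1. Reconcile the DLT texts in Section 6 (Safety Lead-ins, device dose modifications, radiotherapy without interruptions, temozolomide modifications) and Section 7a into one definition, used for both the stopping rules and the primary endpoint. State how a TTFields break or reduction and a temozolomide discontinuation are counted, and whether the one-month device criterion stands alone or adds to the list. Which grades, durations and consequences for the patient apply is for the clinical team.
2. Correct the synopsis so that each look is held when every patient in the cohort has completed the 8-week window or has had a DLT, in line with Sections 6 and 8. Align the wording in Section 7a.

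Cost: protocol wording, and each look up to 4 weeks later than the synopsis states, which Section 8 already requires. No visits are added, because the Day 106 assessment is already scheduled.
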